**Updated and Finalized Statistical
Analysis Plan of the ‘PROtective
Ventilation with Higher Versus Lower
PEEP During One–lung Ventilation
for THORacic Surgery’ (PROTHOR)
Randomized Clinical Trial**

The PROTHOR–investigators

INTRODUCTION

The 'PROtective Ventilation with High versus Low PEEP during One-lung Ventilation for THORacic surgery' (PROTHOR) randomized clinical trial compares an intraoperative ventilation strategy with higher positive end-expiratory pressure (PEEP) with recruitment maneuvers ('higher PEEP') to a conventional strategy consisting of lower PEEP of 5 cmH₂O without recruitment maneuvers ('lower PEEP'), both with low tidal volumes.¹ The primary objective of this study is to determine whether 'higher PEEP' is superior to 'lower PEEP' with regard to the incidence of postoperative pulmonary complications (PPC). Enrollment of patients in the PROTHOR study is progressing well and the study is planned to enroll the last patient in the second trimester of 2024.

To prevent outcome reporting bias and data-driven analysis results, the International Conference on Harmonization of Good Clinical Practice (ICH-GCP) recommends that clinical trials should be analyzed according to a pre-specified detailed Statistical Analysis Plan (SAP). This document presents the updated and finalized SAP of the PROTHOR study.

METHODS

Design, ethics and registration

The PROTHOR study is an international, multicenter, parallel, two–group, prospective, randomized, patient and outcome–assessor blinded superiority clinical trial designed to determine if an intra–operative higher PEEP strategy is superior to a lower PEEP strategy with respect to the development of PPC in adult patients submitted to thoracic surgery requiring one–lung ventilation (OLV).

The protocol, with a detailed description of the study population, the two strategies and follow–up plan of the PROTHOR trial were previously published elsewhere.¹ The PROTHOR study is registered at clinicaltrials.gov (study identifier NCT02963025) and was approved by the Ethical Committee of the Istanbul University, Medical Faculty, Turkey (2016/483, April 8, 2016). Additionally, the institutional review board at the University Hospital Dresden, Technische Universität Dresden, Dresden, Germany, approved the study on 23.09.2016 (reference no. EK 392092016). The respective review boards of participating sites approved the study as well.

Randomization and blinding

Eligible patients are randomly allocated in a 1:1 ratio to the ‘higher PEEP’ or ‘lower PEEP’ strategy. The allocation sequence is computer–generated by an independent investigator using permuted blocks of random size of four, six, and eight patients, and stratified per center. Randomization is performed by local investigators patient–by–patient employing a dedicated, password protected, SSL–encrypted website.

At each site, at least two investigators are involved with the study. One local investigator randomizes the patients immediately before surgery, and is

responsible for the trial intervention and data collection. A second local investigator remains blinded to the assigned treatment, and is responsible for postoperative data collection.

Outcomes

The primary study outcome is a collapsed composite of PPC developing within the first five postoperative days. This endpoint follows the European Perioperative Clinical Outcome (EPCO) definition and has been used before in several clinical trials.²⁻⁴ A patient that develops one or more PPCs is considered as meeting the primary outcome. The components of the composite outcome of PPC have been defined and described elsewhere,¹ and include: 1) aspiration pneumonitis; 2) moderate respiratory failure; 3) severe respiratory failure; 4) acute respiratory distress syndrome (ARDS); 5) pulmonary infection; 6) atelectasis; 7) cardiopulmonary edema; 8) pleural effusion; 9) pneumothorax on the non-surgical lung; 10) pulmonary infiltrates; 11) prolonged air leakage; 12) purulent pleuritic; 13) pulmonary embolism; and 14) lung hemorrhage. The selected PPC can sensibly be merged as they share common pathophysiological mechanisms and have plausibility to be affected in the same direction by the intervention tested in this study.

Secondary outcomes include: 1) extended PPC, including bronchospasm or mild respiratory failure; 2) severe PPC, as defined in a recent published clinical trial⁵ (composite of severe respiratory failure, pneumothorax, ARDS, pulmonary infection, prolonged air leakage, purulent pleuritis, new requirement of non-invasive or invasive ventilation due to respiratory failure and/or atelectasis); 3) a composite outcome of intraoperative complications, including use of continuous positive airway pressure for the non-ventilated lung, use of inhaled nitric

oxide/prostacycline, use of selective fiberoptic insufflation, hypotension unresponsive to fluids and/or vasoactive drugs, new arrhythmias unresponsive to intervention, need for high dosage of vasoactive drugs, need for massive transfusion, life-threatening surgical complication (including major bleeding, tension pneumothorax and intracranial injury), hypoxemia and hypercapnia rescue maneuvers; 4) postoperative extrapulmonary complications, including systemic inflammatory response syndrome, sepsis, severe sepsis, septic shock, extrapulmonary infection, coma, acute myocardial infarction, acute renal failure, disseminated intravascular coagulation, stroke, hepatic failure, and gastrointestinal failure; 5) need for unexpected intensive care unit admission or readmission; 6) any postoperative respiratory intervention used for respiratory failure (new requirement of non-invasive ventilation or mechanical ventilation); 7) number of hospital-free days at day 28; 8) in-hospital mortality; 9) 90-day mortality; 10) arterial blood gas analysis during surgery (PaO₂, PaCO₂, pH_a). All definitions are available in **Table 1**.

Cleaning and closing of the database

The database will be locked as soon as all data are entered and all discrepant or missing data are resolved, after all efforts are employed to fix missing data, complete the database, and we consider that the remaining issues cannot be fixed. At this step, the data will be reviewed before database locking. After locking, the data will be exported for statistical analysis. At this stage, permission for access to the database will be removed for all investigators, and the database is archived.

Missing data

No or minimal losses to follow-up for the primary outcome is anticipated. Complete-case analysis will be carried out for all outcomes. However, if more than 5% of missing data is found for the primary outcome, a sensitivity analysis using multiple imputations and estimating-equation methods will be carried out. Multiple imputation will consider imputation models based on prognostic baseline and post-baseline variables under a missing at random assumption.

Sample size

An adaptive trial design is used, which accumulates data and uses external information to modify aspects of the design without undermining the validity and integrity of the trial. The group sequential methods design offers the possibility for early stopping the study if the experimental treatment shows a statistically significant therapeutic advantage at an interim assessment, but also allows early stopping for futility if the interim analysis reveals that, with high probability, the trial will be negative.

PROTHOR is designed to enroll a total of 2378 patients (1189 in each arm). This number allows the detection of a reduction in the incidence of the primary outcome from 23% in the 'lower PEEP' group to 17.25% in the 'higher PEEP' group (relative risk reduction of 25%), considering a type I error of 5%, a power of 90%, similar allocation ratio between the arms (1:1) and a dropout rate of 5%. The required sample size is calculated based on an estimated effect size derived from individual patient data from previous trials,^{3,4,6-9} and the LAS VEGAS study.¹⁰

An alpha-spending function was used to generate efficacy boundaries and a beta-spending function to generate futility boundaries (gamma family spending function, type I error 0.05, type II error 0.1). By using a gamma of -4 for the alpha

and gamma of -2 for the beta spending function a moderate hurdle for early stopping for efficacy and a reasonable chance to stop early due to futility is considered. A non-binding futility boundary was constructed in such a way that it can be overruled if desired without inflating the type 1 error. This flexibility is important, since the data monitoring committee might well prefer to keep the trial going to gather additional information, despite crossing the futility boundary (**Figure 1** and **Table 2**).

Interim analyses

Five interim assessments for evaluation of efficacy, harm, and/or futility were planned, with the aim of possibly stopping the study early. The planned number of assessments describes the number of time points, including the closing date of the study, at which the investigator plans to analyze the thus far collected data. The spacing of assessments will be equal. Therefore, interim analyses were performed after 20% (476 patients), 40% (952 patients), 60% (1426 patients), and 80% (1902 patients) of the planned inclusions, and the final analysis will be performed after 2378 patients (100%) are included (**Table 2**).

Statistical analyses

All statistical analyses will be conducted on an intention-to-treat basis, with patients analyzed according to their assigned treatment arms, except for cases lost to follow up or withdrawal of informed consent. In addition, a per-protocol analysis will be conducted. Variables will be expressed as counts and percentages, means and standard deviations (SD), or medians and interquartile ranges (IQR) whenever appropriate.

The study was designed to detect a difference in the primary outcome with 90% power, using a two-sided superiority hypothesis test with a significance level

of 0.0428 (correspondent to the Z-value of 2.025 for efficacy or futility in the final analysis in **Table 2**) and presented with a two-sided 95% confidence interval. Secondary outcomes will be assessed using a two-sided superiority hypothesis test with a significance level of 0.05 and presented with a two-sided 95% confidence interval. In addition to the unadjusted p values for secondary outcomes, a Holm-Bonferroni procedure will be applied to control for multiple testing.¹¹ Analyses will be performed using the software R (R Core Team, 2016, Vienna, Austria). A list of proposed tables and figures is in **Table 3**.

Trial profile

Patient flows will be represented in a CONSORT flowchart (**Proposed Inserts**).

Baseline characteristics

A description of the baseline characteristics of the trial participants will be presented by treatment group (**Proposed Inserts**). Discrete variables will be summarized as numbers (%). Percentages will be calculated according to the number of trial participants for whom data are available. Whenever values are missing, the denominator will be stated in the table and no assumptions or imputations will be made. Continuous variables will be summarized by either mean and standard deviation (SD) or median and interquartile range (IQR), according to the observed distribution of the variable.

Adherence to study protocol and ventilatory variables

Surgical and perioperative characteristics will be reported (**Proposed Inserts**). Ventilatory variables and vital signs will be reported after intubation, one hour, and in the last hour of surgery and compared between the two groups. Absolute differences between groups will be calculated using median regression for continuous variables (reported as median difference) and generalized linear

models with binomial distribution and an identity link for binary variables (reported as difference in percentages). Plots comparing ventilatory variables and vital signs among the groups during the first three hours of surgery and in the last hour will be drawn (presenting the data as mean and 95% confidence interval in each time point).

Other daily characteristics

Daily variables will be reported according to the description in **Proposed Inserts**. Absolute differences between groups will be calculated using median regression for continuous variables (reported as median difference) and generalized linear models with binomial distribution and an identity link for binary variables (reported as difference in percentages). Plots comparing daily variables among the groups will be constructed (presenting the data as mean and 95% confidence interval in each time point).

Primary outcome

The effect of 'higher PEEP' compared to 'lower PEEP' on the incidence of PPC will be assessed using a mixed-effect generalized linear model with binomial distribution and identity link, with sites included as random effects to account for the clustering effect and reported as absolute difference with a two-sided 95% confidence interval. Results will be presented in a table of outcomes (**Proposed Inserts**).

Secondary outcomes

For binary outcomes, the effect of 'higher PEEP' compared to 'lower PEEP' will be assessed using a mixed-effect generalized linear model with binomial distribution and identity link, with sites included as random effects to account for the clustering effect and reported as absolute difference with a two-sided 95%

confidence interval. For continuous outcomes, the comparison will be made using a mixed-effect median regression with sites also including as clustering effect, and reported as median difference with a two-sided 95% confidence interval. 90-day mortality will be assessed using Kaplan–Meier curves, and hazard ratios with 95% confidence intervals will be calculated with (shared-frailty) Cox proportional hazard models without adjustment for covariates and including sites as frailty. The proportional hazard assumptions will be tested using scaled Schoenfeld residuals and alternative parametric survival models will be used if the proportionality assumption is not sustained. In addition, a Holm–Bonferroni correction to control the family-wide error rate to the p values for all secondary outcomes will be done and presented in a Table.

Per-protocol analysis

The per-protocol population will consist of patients truly ventilated according to the protocol. Thus, patients will be excluded from this population if receiving PEEP < 10 cm H₂O in the ‘higher PEEP’ group or PEEP > 5 cm H₂O and FiO₂ < 1.0 in the ‘lower PEEP’ group, unless rescue for hypoxemia or hypercapnia required adjustments of PEEP and FiO₂ as defined by the protocol.

Subgroup analysis

Treatment effects on incidence of PPC will be analyzed according to the following predefined subgroups: 1) type of surgery (non-thoracoscopic versus thoracoscopic); 2) positioning (lateral decubitus versus supine position); 3) baseline SpO₂ < 96% versus SpO₂ ≥ 96%; 4) chronic obstructive pulmonary disease (COPD) versus non-COPD; 5) body mass index < 30 kg/m² versus ≥ 30 kg/m²; and 6) duration of one-lung ventilation < 120 versus ≥ 120 minutes. Analyses of heterogeneity of effects across subgroups will be performed with the

use of treatment-by-subgroup term added to the primary model and will be presented in a forest plot.

Other exploratory analyses

Given that the primary outcome of the present study is a collapsed composite, the choice of the statistical method is an important part of designing since various methods provide different power, depending on the situation. In addition to the standard analysis described above, the following analyses will be performed:

- Count analysis: the number of positive component events (i.e., 'count') across the composite will be assessed. The groups will be compared on the count using a Wilcoxon rank sum test, and the odds ratio with the 95% confidence interval will be assessed with a cumulative logistic regression model;
- Individual component analysis: the effect of the intervention in each component will be analyzed estimating the risk ratio and confidence intervals with Wald's likelihood ratio approximation test using a Bonferroni correction for multiple comparisons. The 99.6% Bonferroni-corrected confidence intervals will be reported ($1 - 0.05/14 = 0.996$);
- Common effect test: A multivariate (i.e., multiple outcomes per subject) generalized estimating equations (GEE) model will be used to estimate a common effect odds ratio across the components;

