Abbreviation: PEEP is positive end-expiratory pressure; PBW is predicted body weight; FiO₂ is inspired fraction of oxygen; SpO₂ is pulse oximetry; etCO₂ is end-tidal carbon dioxide.

Table 3 – Primary and Secondary outcomes

	Higher PEEP (n =)	Lower PEEP (n =)	Absolute Difference (95% CI)	p value
Primary outcome				
Postoperative pulmonary complications – no. (%)				
Aspiration pneumonitis				
Moderate respiratory failure				
Severe respiratory failure				
Acute respiratory distress syndrome				
Pulmonary infection				
Atelectasis				
Cardiopulmonary edema				
Pleural effusion				
Pneumothorax				
Pulmonary infiltrates				
Prolonged air leakage				
Purulent pleuritic				
Pulmonary embolism				
Lung hemorrhage				
Secondary outcomes				
Extended postoperative pulmonary complications – no. (%)				
Mild respiratory failure				
Bronchospasm				
Intraoperative complications – no. (%)				
CPAP for the non-ventilated lung				
iNO, prostacycline or selective fiberoptic insufflation				
Hypotension unresponsive to fluids or vasoactive drugs				
New arrhythmias unresponsive to intervention				

PROTHOR Statistical Analysis Plan (v1.0, January 17th, 2024)

Need for high dosage of vasoactive drugs
Need for massive transfusion
Life-threatening surgical complication*
Hypoxemia rescue maneuvers
Hypercapnia rescue maneuvers
Postoperative extrapulmonary complications – no. (%)
Systemic inflammatory response syndrome
Sepsis
Severe sepsis
Septic shock
Extrapulmonary infection
Coma
Acute myocardial infarction
Acute renal failure
Disseminated intravascular coagulation
Stroke
Hepatic failure
Gastrointestinal failure
Unexpected ICU admission or readmission – no. (%)
Postoperative respiratory intervention – no. (%)
Non-invasive ventilation
Invasive ventilation
Number of hospital-free days at day 28
All-cause hospital mortality – no. (%)
90-day mortality – no. (%)

Data are median (quartile 25th - quartile 75th) or N / total (%).

Abbreviations: PEEP is positive end-expiratory pressure; CPAP is continuous positive airway pressure; iNO is inhaled nitric oxide; ICU is intensive care unit.

* Including major bleeding, tension pneumothorax and intracranial injury.

eTable 2 – Additional Baseline Characteristics

	Higher PEEP (n =)	Lower PEEP (n =)
Cumulated ambulation score		
Transfer from supine-to-sitting-to-supine – no. (%)		
Unable to perform function despite assistance from 2 people		
Only able to perform function with assistance from 1 or 2 people		

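### The primary test uses a level of 0.0428 but is reported with an unlabelled 95% interval, and the identity-link mixed model behind it can fail to fit with no fallback named

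*SAP*

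**What the plan says.** **Level and interval.** Under Statistical analyses, the final primary test is two-sided at a level "of 0.0428 (correspondent to the Z-value of 2.025 for efficacy or futility in the final analysis", and the same sentence says that the result is "and presented with a two-sided 95% confidence interval". The Primary outcome section, the update column of the modifications table and the Table 3 shell, headed "Absolute Difference (95% CI", all repeat 95%. The overall design is stated as "considering a type I error of 5%, a power of 90%, similar allocation ratio between the arms (1:1) and a dropout rate of 5" percent.

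**Model.** The primary outcome is analysed with a "mixed-effect generalized linear model with binomial distribution and identity link". Site enters as a random effect, and the absolute difference is reported with a 95% interval. The binary secondary outcomes use the same model. The subgroup tests make "use of treatment-by-subgroup term added to the primary model". On computation, the SAP says only that R will be used. It gives no fitting routine, convergence rule, number of sites or between-site variance. For 90-day mortality it does provide that "alternative parametric survival models will be used if the proportionality assumption is not sustained".

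**The concern.** **Interval.** Alpha is spent at four earlier looks, so the final test needs |Z| above 2.025. A 95% interval corresponds to 1.96. Readers judge the headline effect by its interval, and this one is narrower than the trial's own error rate allows. Nothing in the SAP marks it as unadjusted. For its exploratory component analysis the SAP does match the interval to the corrected level (99.6%), so the primary outcome is treated less carefully than its components.

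**Model.** With an identity link, normal site effects are added directly to a risk. Some site risks can then fall below 0, where the binomial likelihood is undefined, and a maximum-likelihood fit can stop with an error. If that happens, the analyst must pick a substitute with the data in hand. Reasonable substitutes do not always agree on significance, and the Introduction says that the SAP exists to keep the results from steering the analysis.

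**Working it through.** **1. The SAP's own level.** Inputs from Table 2: five equally spaced looks, two-sided alpha 0.05, gamma spending with parameter -4, non-binding futility. Numerical integration gives boundaries 3.253, 2.986, 2.692, 2.374 and 2.0253, against 3.252, 2.986, 2.692, 2.374 and 2.025 in Table 2. The final nominal level is 2(1 - Φ(2.0253)) = 0.0428. The SAP's figure is correct.

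**2. The matching interval.** 2Φ(2.025) - 1 = 0.957, so the level is 95.7%. The width ratio is 2.025/1.96 = 1.033.

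Half-width at the design rates, with 2259/2 = 1129.5 per arm:
- SE = √[(0.23×0.77 + 0.1725×0.8275)/1129.5] = 1.683 points
- 1.96 × 1.683 = 3.30 points
- 2.025 × 1.683 = 3.41 points

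**3. Where test and interval disagree.** Solving d = z × SE(d) for 23% versus 23% - d gives d = 3.375 points at z = 1.96 and 3.483 at z = 2.025. Between these, the test is non-significant and the 95% interval excludes zero.

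Probability of 1.96 < |Z| < 2.025 at the final look, using the Table 2 boundaries:

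| True difference | Efficacy/harm stopping only | Futility stopping also followed |
|---|---|---|
| 0 | 0.63% | 0.21% |
| 2.875 points (half the design effect) | 2.17% | 1.43% |
| 5.75 points (design effect) | 0.83% | 0.55% |

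Overall type I error is 0.0500 with 2.025 at the final look and 0.0563 with 1.96.

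**4. Why the identity link can fail.** If site risks are normal around 17.25% with standard deviation s, the share below 0 is Φ(-17.25/s). The values of s and the site counts are assumptions.

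| s (points) | Share of site risks below 0 | At least one such site in 20 / 70 |
|---|---|---|
| 5 | <0.1% | 1% / 2% |
| 8 | 1.6% | 27% / 67% |
| 10 | 4.2% | 58% / 95% |

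**5. Simulated fits.** R lme4 with identity link, 2259 patients, 23% versus 17.25%, normal site effects with SD 0.2 or 0.5 on the logit scale, 40 trials per setting. At the mean risk of 20.1% these SDs are about 0.161 × 0.2 = 3 points and 0.161 × 0.5 = 8 points. Unequal sites have exponential weights.

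| Assumed sites | Stopped with an error: SD 0.2 | SD 0.5 | Pooled |
|---|---|---|---|
| 25 equal | 0/40 | 0/40 | 0/80 |
| 60 equal | 11/40 | 19/40 | 30/80 |
| 25 unequal | 20/40 | 31/40 | 51/80 |
| 60 unequal | 40/40 | 39/40 | 79/80 |

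For an assumed 2% outcome (25 equal sites at SD 0.2; 60 unequal at SD 0.5), 79 of 80 stopped. Supplying start values barely helped: 0, 29, 47 and 78 of 80, and 79 of 80 for the 2% outcome. Logit mixed models and identity-link quasi-likelihood ran in all 400.

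**6. Effect of leaving the substitute open.** Four substitutes were compared at Z = 2.025: raw difference, Mantel-Haenszel difference, standardised logit difference and identity-link quasi-likelihood. Each setting has 300 trials with unequal sites, SD 0.5 and no interim stopping.

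| Setting | Any of the four disagree | Quasi-likelihood vs standardised logit |
|---|---|---|
| 60 sites, half effect | 35/300 (11.7%) | 22/300 |
| 25 sites, half effect | 32/300 (10.7%) | 22/300 |
| 60 sites, design effect | 13/300 (4.3%) | 9/300 |

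The mean absolute gap between the last two estimates was 0.31 to 0.35 points.

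**The case against.** **Interval.** The decision rule is explicit, the interval is correctly called 95%, and a p-value stands beside it in the shell. The 0.056 arises only if the written rule is ignored, and the width differs by about a tenth of a point. All of this stands and keeps the point small. It does not remove the mismatch or supply the missing label.

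**Model.** The failure rates are not properties of this trial, because site number, sizes and spread are assumed. They also depend on the algorithm. A separate quadrature fit with uneven sites reached the zero-risk boundary in only 13 to 15% of runs at a spread of 3 points, though in 68 to 80% at 6 points. Quasi-likelihood always ran, and it arguably falls within the SAP's wording. So the defect is that the routine and the failure rule are unspecified, not that the model cannot be estimated.

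Three further limits also stand. The mortality provision deals with a violated assumption, not with non-convergence, so it is only a loose parallel. The disagreement figures are not restricted to trials where the fit failed, and none was computed under the null, so type I error inflation is not shown. Fitting could be tried on arm-masked data before unblinding, but the SAP does not plan this.

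Nothing else in the SAP fills the gap. Its estimating-equation analysis applies only if more than 5% of primary outcome data are missing, and the risk-ratio and chi-square analysis was replaced, not kept as a backup.

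**Conclusion.** Both parts hold, and both should be fixed before unblinding.

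- **Interval:** a direct mismatch within one sentence. It is small: about 3% in width, with test and interval disagreeing in 0.2% to 2.2% of trials over the effects examined. The 0.0428 boundary itself is correct.
- **Model:** a real gap in pre-specification for the primary outcome, the binary secondary outcomes and the subgroup tests. Failure is a risk of unknown size. It was absent with 25 equal sites and nearly universal with 60 unequal sites or a 2% outcome, all under assumed site structures and one fitting routine. If a substitute has to be chosen late, the choice can change the significance verdict in a minority of trials.

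**What to change.** 1. **Interval.** Report the primary difference with a 95.7% interval (estimate ± 2.025 SE, which is also the repeated confidence interval at the final look). Change Statistical analyses, Primary outcome, the update column of the modifications table, and the primary row of the Table 3 shell. If the 95% interval is kept, label it as unadjusted for the interim looks.
2. **Routine and fallback.** Name the R routine. Before unblinding, name one fallback for when the identity-link fit stops with an error or does not converge: a logistic mixed model with a random site intercept. Average each patient's predicted risk under both arms, with site effects at their predicted values. Report the absolute risk difference with a delta-method SE and a bootstrap check.
3. **Scope.** Apply the same rule to the binary secondary outcomes. For subgroups, use the same fallback and standardise within each subgroup. Making this model primary would also be sound.

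The estimand stays the absolute difference. In the simulations the mean standardised difference was within 0.07 points of the mean raw difference in every setting. The 95.7% delta-method interval covered the truth in 97.7%, 95.7% and 96.3% of trials.

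The cost is SAP wording and a few lines of R. The primary half-width goes from 3.30 to 3.41 points at the design rates. Sample size and data collection do not change.
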